# 4.3 Number of Study Centers

This study will open at the Huntsman Cancer Institute. If additional recruitment is required this will become a multi-center trial.

# 4.4 Study Duration

1 year and 3 months for enrollment, 3 years for study completion.

# 5 ELIGIBILITY CRITERIA

This eligibility checklist is used to determine patient eligibility and filed with the enrolling investigators signature in the patient research chart.

Patient No. \_\_\_\_\_ Patient's Initials: (L,F,M)

5.1 Inclusion Criteria

# Yes/No (Response of "no" = patient ineligible)

- **5.1.1** Patients must be  $\geq 18$  years or older.
- **5.1.2** Patients must have stage IIIB, IIIC, or IVM1a (equivalent staging at time of enrollment via AJCC 7th edition) metastatic melanoma which is eligible for complete surgical resection.
- **5.1.3** Prior systemic, regional and radiation anticancer therapies must have been completed at least three months prior to enrollment. Prior therapies (including anti-PD-1 inhibitors) are allowed provided three months have elapsed from last dose.
- **5.1.4** Patients must be a candidate for intralesional therapy.
  - At least 1 injectable cutaneous, subcutaneous, or nodal melanoma lesion  $\geq 10$  mm in longest diameter

OR

• Multiple injectable melanoma lesions which in aggregate have a longest diameter of  $\geq 10$  mm

AND

- Must have no known bleeding diathesis or coagulopathy that would make intratumoral injection unsafe.
- **5.1.5** Patients must have an Eastern Cooperative Oncology Group (ECOG) performance status of 0 or 1.
- **5.1.6** Serum LDH level  $\leq$  1.5 upper limit of normal (ULN) within 28 days prior to enrollment.
- **5.1.7** Patients have adequate organ function within 28 days prior to enrollment, as defined in table 1 listed below.

Table 1: Adequate Organ Function Laboratory Values:

Protocol name: Phase II Neoadjuvant trial of Nivolumab in Combination with HF10 Oncolytic Viral Therapy in Resectable Stage IIIB, IIIc, IVM1a Melanoma (Neo-NivoHF10) Version Date: 22JUL2019 Principal Investigator: [name]

System	Laboratory Value
Hematological:	
Absolute Neutrophil Count ANC	≥ 1,500/uL
Platelets	≥ 100,000/uL
Hemoglobin	$\geq$ 9 g/dL
Renal	
Serum Creatinine OR measured calculated creatinine clearance (GFR may also be used in place of creatinine or CrCl)	$\leq$ 1.5 upper limit of normal (ULN) OR $\geq$ 60 mL/min for subject with creatinine levels $\geq$ 1.5 X institutional ULN
Hepatic	
Serum total bilirubin	$\leq$ 1.5 X ULN OR Direct bilirubin $\leq$ ULN for subjects with total bilirubin $\geq$ 1.5 ULN
AST or ALT	
 
≤ 2.5 X ULN OR
 
≤ 5 X ULN for subjects with liver metastases
 

- **5.1.8** Men and women of childbearing potential must agree to use adequate contraception from the time of consent through 7 months after final nivolumab study treatment.
- **5.1.9** \_\_\_\_\_ Females of childbearing potential must have a negative urine or serum pregnancy test within 1 week prior to the start of treatment.
- **5.1.10** Patients must be able to provide informed consent and willing to sign an approved consent form that conforms to federal and institutional guidelines.

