#### **1.2.2** Assess overall survival

Endpoint: patients will be followed for survival for one year after completion of adjuvant nivolumab.

**1.2.3** Assess the response of tumors prior to surgery based on RECIST 1.1

Endpoint: patients will be assessed radiographically with CT or MRI scan or assessed clinically.

**1.2.4** Assess complete surgical resection

Endpoint: patients will be assessed at surgery to determine if complete surgical resection was achievable after neo-adjuvant treatment with nivolumab and HF10.

**1.2.5** Assess the safety and tolerability of neoadjuvant nivolumab and HF10 with adjuvant nivolumab in patients with metastatic melanoma.

Endpoint: patients will be monitored for adverse events (AEs) and serious adverse events (SAEs) related to either or both nivolumab and HF10.

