#### Clinical Studies with HF10 + Ipilimumab in unresectable melanoma

# Phase 2 multicenter trial to evaluate efficacy and safety of HF10 oncolytic virus immunotherapy and ipilimumab in patients with unresectable stage IIIB-IV melanoma in the US (Protocol T14-10682, IND No 13,342)

An ongoing phase 2 trial of HF10 and ipilimumab in unresectable metastatic melanoma patients is assessing whether the antitumor effect of HF10 is enhanced by concurrent ipilimumab treatment. Ipilimumab naïve adults with Stage IIIB, IIIC or IV unresectable melanoma with measurable non-visceral lesion(s) received HF10

injections into single or multiple tumors  $(1 \times 10^7 \text{ TCID}_{50}/\text{mL}, \text{ up to } 5 \text{mL/dose}); 4$ injections every week; then up to 15 injections every 3 weeks. Ipilimumab infusions (3 mg/kg) were given every 3 weeks for 4 doses. Tumor responses were assessed at 12, 18, 24, 36, and 48 wks. Best Overall Response Rate (BORR) was determined at 24 wks. Of 46 pts treated, 20% were stage IIIB, 43% stage IIIC, and 37% stage IV. Most HF10-related AEs were  $\leq$  Grade 2, similar to HF10 monotherapy. No DLTs were reported; 3 Grade 4 AEs reported, all not treatment related. 30.4% had Grade 3 AEs. HF10-related Grade 3 AEs (n=3) were left groin pain, thromboembolic event and lymphedema, hypoglycemia, and diarrhea. Twenty-one (46%) patients had received at least 1 prior therapy for metastatic melanoma. Of 43 efficacy evaluable patients, preliminary BORR at 24 weeks per irRC was 41.8% (11.6% CR, 30.2% PR), disease stability rate 67.4% (25.6% SD). Eight responders (53%) were Stage IV. Overall study BORR, including those after 24 weeks, by irRC was 47.7% (15.9% CR, 31.8% PR), disease stability was 65.9% (18.2% SD). In summary, HF10 in combination with ipilimumab treatment does not appear to exacerbate ipilimumab toxicity, is safe, well tolerated and has both local and systemic antitumor activity. The efficacy appears greater than that seen with ipilimumab monotherapy. Since the clinical trial is on-going, the final results of the trial are still pending.

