# 9.4 **Neo-Adjuvant Therapy Tumor Response**

Clincal (radiographic or physical exam) Response to neo-adjuvant therapy will be assessed by RECIST 1.1. The following definitions and criteria should be used for the baseline evaluations of existing disease, and for the ongoing evaluation of tumor responses prior to surgery.

**Measurable lesions** - lesions that can be accurately measured in at least one dimension with longest diameter (LD)  $\geq 10$  mm using CT, MRI, or caliper or ruler measurements or  $\geq 20$  mm with x-ray. A lymph node must be  $\geq 15$  mm in short axis when assessed by CT scan

**Non-measurable lesions** - all other lesions including small lesions (LD < 10 mm with CT, MRI, or caliper measurements or <20 mm with x-ray).

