# Documentation of "Target" and "Non-Target" Lesions

- All measurable lesions up to a maximum of two lesions per organ and five lesions in total, representative of all involved organs should be identified as *target lesions* and recorded and measured at baseline.
- Target lesions should be selected on the basis of their size (lesions with the longest diameter) and their suitability for accurate repeated measurements (either by imaging techniques or clinical assessments).
- A sum of the LD for *all target lesions* will be calculated and reported as the baseline sum LD. The baseline sum LD will be used as the reference by which to characterize the objective tumor response.
- All other lesions (or sites of disease) should be identified as *non-target lesions* and should also be recorded at baseline. Measurements of these lesions are not required, but the presence or absence of each should be noted throughout follow-up.

	Evaluation of target lesions
Complete Response (CR)	Disappearance of all target lesions (Must persist for a minimum of four weeks)
Partial Response (PR)	At least a 30% decrease in the sum of the LD of target lesions, taking as reference the baseline sum LD (Must persist for a minimum of four weeks)
Progressive Disease (PD)	At least a 20% increase in the sum of the LD of target lesions, taking as reference the smallest sum LD recorded since the treatment started or the appearance of one or more new lesions

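### Sections 5.1.4 and 9.4 disagree on lesion size, so some eligible patients may have no RECIST target lesion and no route to an overall response other than PD; nodes qualify on one axis and are summed on another

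*Combined protocol and SAP*

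**What the plan says.** Secondary objective 1.2.3 is to "Assess the response of tumors prior to surgery based on RECIST 1.1". Its endpoint says that "patients will be assessed radiographically with CT or MRI scan or assessed clinically".

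Section 5.1.4 accepts either of two lesion conditions. The first is "At least 1 injectable cutaneous, subcutaneous, or nodal melanoma lesion" of at least 10 mm longest diameter. The second is "Multiple injectable melanoma lesions which in aggregate have a longest diameter of" at least 10 mm, with no minimum per lesion. No other criterion asks for measurable disease. The HF10 volume table in section 6.1.1 has rows for lesions of 0.5 cm or less and of 0.5 to 1.5 cm, so small lesions are expected.

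Section 9.4 defines measurable disease as "lesions that can be accurately measured in at least one dimension with longest diameter (LD") of at least 10 mm by CT, MRI, caliper or ruler. For a lymph node the threshold is at least 15 "mm in short axis when assessed by CT scan". All other lesions are non-measurable. Target lesions come only from measurable ones. Non-target lesions are recorded as present or absent.

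For target lesions, "The baseline sum LD will be used as the reference by which to characterize the objective tumor response". The text makes no exception for nodes in that sum. Target CR is disappearance of every target lesion.

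Section 10 gives no analysis set, denominator or method for RECIST response.

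**The concern.** The entry rule and the response rule use different size tests. A patient can pass the first and have nothing that the second can measure. Such a patient has no baseline sum, so PR and target-lesion PD cannot be calculated. The overall-response table does not say what to record if the small lesions stay stable or vanish.

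The nodal rule has a separate problem: it uses the short axis for entry to the target set and the longest diameter for every later calculation.

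At stake are the pre-surgical response rate (1.2.3) and the concordance with irRC (1.3.2), which needs a RECIST category for each pair. Note 19 of the Study Calendar also makes RECIST the clinical response criterion used in treatment decisions. With 20 patients, each one moves a rate by 5 percentage points (1/20). If the handling is not fixed in advance, it will be chosen once results are known.

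**Working it through.** **The plan's own figure.** Section 10 states 59% power at a true pathologic response rate of 20% and 89% at 30%, with 20 patients, a null of 5% and rejection at 4 or more responses. The exact binomial gives P(X ≥ 4) = 58.9% at 20%, 89.3% at 30% and 1.6% at 5%. The stated powers reproduce. They concern the pathologic endpoint and do not depend on this point.

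**Step 1: entry rule against measurability rule.** Hypothetical lesion sets:

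| Longest diameters (mm) | Aggregate | Passes 5.1.4 | Largest lesion | Any lesion ≥ 10 mm (9.4) |
|---|---|---|---|---|
| 5, 5 | 10 | yes | 5 | no |
| 3, 4, 3 | 10 | yes | 4 | no |
| 9, 9 | 18 | yes | 9 | no |
| 4, 4, 4, 4 | 16 | yes | 4 | no |

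A node's short axis cannot exceed its longest diameter. A node with a longest diameter from 10 to under 15 mm therefore passes 5.1.4 and always fails the CT threshold in 9.4. A longer node also fails if its short axis is under 15 mm.

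**Step 2: what such a patient can be recorded as.** The best-overall-response table in 9.4 has seven rows. The CR row, both PR rows and the SD row each require a named target-lesion status. One PD row requires target PD. The last two rows accept any target status, and both give PD. A patient without target lesions therefore fits the table only as PD. Treating an empty target set as target CR does not help: the second row would then score unchanged non-target disease as PR, which cannot be intended. The non-target table does define CR, SD and PD, but nothing carries its CR or SD into an overall response.

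**Step 3: the axis for nodes.** Change = (follow-up − baseline) / baseline; PR needs a decrease of at least 30%. Hypothetical single target nodes, longest diameter × short axis:

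| Baseline → follow-up (mm) | Longest diameter | Short axis |
|---|---|---|
| 24×16 → 18×9 | (18−24)/24 = −25.0%, SD | (9−16)/16 = −43.8%, PR level |
| 30×18 → 20×13 | (20−30)/30 = −33.3%, PR | (13−18)/18 = −27.8%, SD level |

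The category changes in both directions. A target node that shrinks to normal size but remains visible has not disappeared, so it cannot count as CR.

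**Step 4: why the denominator must be stated.** Let k of the 20 patients have no target lesion, and suppose 8 RECIST responders. Both values are assumptions. With measurable patients only as denominator (exact 95% intervals):

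| k | Rate | 95% CI | Width (points) |
|---|---|---|---|
| 0 | 8/20 = 40.0% | 19.1 to 63.9 | 44.8 |
| 2 | 8/18 = 44.4% | 21.5 to 69.2 | 47.7 |
| 4 | 8/16 = 50.0% | 24.7 to 75.3 | 50.6 |
| 6 | 8/14 = 57.1% | 28.9 to 82.3 | 53.4 |

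With all 20 as denominator the rate stays at 40.0%. The plan does not say which figure it would report.

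**The case against.** The strongest reply is that section 5.1.4 defines a candidate for intralesional therapy, not a RECIST-evaluable patient, and that the primary endpoint is pathologic. Both statements are true. A patient admitted on aggregate size may also have a measurable lesion that is not injectable. This limits how often the gap matters but does not close it.

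A second reply is that 9.4 names RECIST 1.1, which may supply the missing rules. That standard is not reproduced in full, so this cannot be judged here. Section 9.4 does set out its own definitions and directs that they be used, and those are the ones that conflict.

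Several stronger readings are tempting but not supported:

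- **A 12 mm node is never measurable.** The 15 mm rule is tied to CT. Section 9.4 also accepts caliper or ruler measurement from 10 mm, so a palpable node might be read as measurable. The text leaves this open.
- **CR is impossible with a nodal target.** A node may vanish on imaging or become impalpable. Only a node that stays visible is barred from CR.
- **irRC fails in the same way.** Section 9.5 gives no lesion-size threshold, and its complete response covers non-measurable lesions too.
- **The response rate is biased downward.** That would require unmeasurable patients to be counted as non-responders, and no denominator is named.
- **Comparison with the HF10 plus ipilimumab trial is spoiled.** That trial enrolled "unresectable melanoma with measurable non-visceral lesion(s"), but it is background. No comparison is planned, and its combination, population, 24-week time point and irRC criterion already differ.

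Confirmed response is also hard to record for a different reason. CR and PR must persist four weeks, while the calendar has one post-baseline RECIST assessment before surgery, at day 84, and surgery follows within 28 days. That is a separate matter and does not resolve this one.

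**Conclusion.** The point holds in a limited form. Followed as written, 5.1.4 and 9.4 allow eligible patients who have no target lesion, and for them the overall-response table offers PD or nothing. For CT-assessed nodes, the change of axis between qualification and summation can alter the response category, and the disappearance rule withholds CR from a node that normalises but stays visible.

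One secondary objective (1.2.3) and the RECIST side of one exploratory objective (1.3.2) are affected. The pathologic primary endpoint, the 20 patients and the stated power are unchanged. The documents do not give the number of patients affected, so neither a direction nor a size of bias can be claimed. The lesion sizes, the 8 responders and the values of k in the working are illustrations. The correction is worth making before any response data are reviewed.

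**What to change.** Change the wording of 9.4 and 9.5:

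1. Define a RECIST-evaluable set of patients with at least one target lesion at baseline. Compute the RECIST response rate and the RECIST/irRC concordance in that set.
2. Add non-target-only rows to the best-overall-response table, so that the remaining patients are reported separately as CR, non-CR/non-PD or PD.
3. For nodal target lesions, use the short axis for qualification, for baseline and follow-up sums, and for CR. Replace disappearance with a stated short-axis cut-off, to be set by the sponsor.
4. Say whether the 15 mm rule also applies to nodes measured clinically.

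Eligibility, scans and visits stay as they are. The cost is a RECIST denominator that may fall below 20. In the illustration above, the interval widens from 44.8 points at 20 patients to 47.7 at 18 and 53.4 at 14.

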# 5.2 Exclusion Criteria

Yes/No (Response of "yes" = patient ineligible)

- **5.2.1** Patients with active visceral, central nervous system, or any bone metastases melanoma (Stage IVM1b or IVM1c).
- **5.2.2** Patients whose primary diagnosis was ocular melanoma
- **5.2.3** Patients receiving anti-herpes medication (i.e., acyclovir, famciclovir, or valacyclovir) within 1 week prior to initiating HF10 treatment. Patients may not require intermittent or chronic systemic (intravenous or oral) treatment with an antiherpetic drug other than intermittent topical use.
- **5.2.4** Patients who have an active herpetic skin lesion(s) or prior complications of HSV-1 infection.
- **5.2.5** Uncontrolled intercurrent illness including, but not limited to, ongoing or active infection, symptomatic congestive heart failure, unstable angina pectoris, cardiac arrhythmia, or psychiatric illness/social situations that would limit compliance with study requirements, as determined by the investigator.
- **5.2.6** Medical history of autoimmune disease (e.g. Crohn's disease, ulcerative colitis) or other disease requiring systemic glucocorticoid or immunosuppressive therapy. Subjects who receive daily steroid replacement therapy serve as an exception to this rule. Daily prednisone equivalent at doses up to 10 mg would qualify.
- **5.2.7** Patients with clinically evident Human Immunodeficiency Virus (HIV), Hepatitis B Virus (HBV), Hepatitis C Virus (HCV), or Epstein-Barr Virus (EBV) infection are excluded
- **5.2.8** Pregnant or breast feeding women; women desiring to become pregnant within the timeframe of the study are also excluded.

#### 6 TREATMENT PLAN

#### 6.1 Administration Schedule

The order in which the patient receives Nivolumab and HF10 is not specified and will be determined based on clinic scheduling.

#### 6.1.1 Neo-adjuvant treatment

#### Nivolumab

Nivolumab 240 mg, IV will be administered over 60 minutes ( $\pm 15$  minutes) as tolerated by the patient, every 14 days starting on day 0. The rate of infusion may be increased to 30 minutes as tolerated. A total of 7 infusions will be administered prior to surgery.

# HF10

HF10 1 x  $10^7$  TCID50/mL will be administered by intratumoral injection to a single or multiple eligible tumors. HF10 will be administered on days 0, 7, 14, 21, 28, 42, 56, 70, and 84 for a total of 9 injections. The volume to be injected will be determined by lesion size (see table below for injection volume by tumor mass) with a maximum volume of 5 mL to be administered on a single treatment day. All eligible tumors except one will be treated with HF10 up to the maximum volume allowed. The untreated tumor will be used as an untreated control lesion.

Lesion Size #	Injection Volume † (Dose * )
>5.0 cm	$\leq 5.0 \text{ mL} (5 \text{x} 10^7 \text{ TCID}_{50})$
>2.5 cm to 5.0 cm	$\leq$ 2.0 mL (2x10  TCID 50 )
>1.5 cm to 2.5 cm	$\leq 1.0 \text{ mL} (1 \times 10^7 \text{ TCID}_{50})$
> 0.5 cm to 1.5 cm	$\leq 0.5 \text{ mL} (5 \text{x} 10^6 \text{ TCID}_{50})$
≤ 0.5 cm	0.1 mL (1x10  TCID 50 )

#Per longer perpendicular diameter

 $\pm$ If the dose level is decreased to  $1 \times 10^6$  TCID50/mL, the recommended injection volumes stated in this table are not to be changed.

\*Administration of maximum volume at 1x10^7 TCID50/mL.

# 6.1.2 Surgery

Surgery will be performed within 28 days of completing neo-adjuvant therapy with nivolumab and HF10. Patients who cannot proceed to surgery will not be evaluable and will be replaced. Patients may be allowed to remain on study treatment at the discretion of the principal investigator.

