# 4.2 Number of Patients

The total number of subjects for all sites is initially planned as 20 patients. The primary endpoint of pathologic response rate, including pCR, is expected to be seen in 20% of patients, hence 4 of the planned 20 patients are expected to have a pathologic response including pCR. Only patients who receive the combination neo-adjuvant treatment, nivolumab and HF10, and have a surgical resection according to the study calendar will be considered evaluable. Patients who discontinue the study before surgery then will be considered non-evaluable and will be replaced per principal investigator discretion.

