#### 6.5 **Duration of Therapy**

Subjects must be withdrawn from the study treatment for the following reasons:

- Subject withdraws consent from the study treatment and/or study procedures. A subject must be removed from the trial at his/her own request or at the request of his/her legally acceptable representative. At any time during the trial and without giving reasons, a subject may decline to participate further. The subject will not suffer any disadvantage as a result.
- Adverse events incurred from intra-tumoral administration of the study agent including but not limited to grade 3 or greater persistent infection, delayed healing, necrosis or ulcer formation.
- Subject is lost to follow-up.
- Death.

Subjects may be withdrawn from the study for the following reasons:

- The subject is non-compliant with study drug, trial procedures, or both; including the use of anti-cancer therapy not prescribed by the study protocol.
- If, in the investigator's opinion, continuation of the trial would be harmful to the subject's well-being.
- The development of a second cancer.
- Development of an intercurrent illness or situation which would, in the judgment of the investigator, significantly affect assessments of clinical status and trial endpoints.
- Deterioration of ECOG performance status to 4.

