# 7.1.2 HF10

In the event that the patient is unable to tolerate HF10 (grade 2 intolerable or higher chills, injection site disorders, fatigue, malaise, pyrexia, nausea, dehydration, pruritus, and/or hypotension which do not respond to optimal management) at the discretion of the treating provider, the dose will be reduced to  $1 \times 10^{6}$  TCID50/mL. The HF10 product will be diluted with physiological saline just before use to meet the target dose level. Specific instructions will be provided in the Pharmacy Manual.

If the patient is unable to tolerate the reduced dose the patient will be withdrawn from treatment.

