6. Biopsies are mandatory at day 0 and surgery. Biopsies are optional at day 42 and progression. See section 13.1 for details about the collection.

7. Adverse events will be followed until resolution while the patient remains on treatment. Events will be followed for 90 post treatment for SAEs and events thought to be related to the study medication will be followed until resolution or stabilization of the adverse event, or until the patient starts a new treatment regimen.

8. Surgery should occur no later than 28 days after D84.

9. Adjuvant nivolumab should be initiated within 90 days after definitive surgery.

10. EOT visit should occur 28 days (+-14 days) after the completion of therapy.

11. Follow-up should occur every three months (+-or 14 days) for 1 years post EOT visit.

12. Surgery will reset the scan schedule and should occur approximately every 12 weeks after surgery as standard of care.

13. Pathology at surgery will be used to determine pathological response.

14. Collection of blood samples for correlatives is optional and will be collected prior to HF10 injection during the neo-adjuvant (days 0,7, 14, 21, 28, 42, 56, 70, 84) and prior to nivolumab infusion during the adjuvant nivolumab administration.

15. Men and women of childbearing potential must agree to use adequate contraception from the time of consent through 7 months after nivolumab study treatment (neoadjuvant and adjuvant). A pregnancy test will be conducted w/in 72 hours prior to beginning adjuvant nivolumab.

16. Next generation sequeencing is required at screening as per standard of care. Testing will include, but is not limited to BRAF mutational analysis.

17. Thyroid Tests will include TSH and free T4. In the event of hypo/hyper thyroidism, appropriate support will be provided in accordance with institutional guidelines.

18. Lesion photography should be completed at each time point AND when a new lesion is identified.

19. irRC and RECIST should be done prior to surgery. Only RECIST will be used as clinical response criteria and used to make treatment decisions

Protocol name: Phase II Neoadjuvant trial of Nivolumab in Combination with HF10 Oncolytic Viral Therapy in Resectable Stage IIIB, IIIc, IVM1a Melanoma (Neo-NivoHF10) Version Date: 22JUL2019 Principal Investigator: [name]

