# 9 CRITERIA FOR EVALUATION AND ENDPOINT

## 9.1 **Pathological response**

The primary objective of this study will be to identify the pathologic response rate at surgery, including complete response, after 12 weeks of neoadjuvant treatment with nivolumab and HF10. Pathologic response rate will be defined based on the quantity of residual viable tumor in the surgical resection specimen at the time of definitive surgery. A percent viable tumor will be assessed semi-quantitatively in the pre treatment biopsy, on study biopsy at day 42 and the definitive surgical resection specimen by estimating the proportion of residual tumor in relation to the total tumor area and reported as percentage viability (Ribero et al 2007) as per institutional practice. A pathologic complete response will be defined as no viable residual melanoma cells in the surgical specimen. A major pathologic response will be defined as <50% viable tumor cells. A minor pathologic response will be defined as 50% or greater viable tumor cells, including specimens that have 100% viability at surgery. Pathologic response rate (pRR) will be defined as frequency of either pCR or a pathologic major response. This will be compared to the viablity values of the tumor at baseline. Biopsies will be required at Day 0 and at surgery to perform this analysis. A patient must complete the neoadjuvant phase of the trial and complete surgery to be considered evaluable for pathological response.

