## 9.8 Complete Surgical Resection

Patients will be assessed at surgery to determine if complete surgical resection was achievable after neo-adjuvant treatment with nivolumab and HF10. Completeness of surgical resection will be defined by standard definitions as follows: R0 indicates all gross clinical disease resected with microscopic pathologic negative margins; R1 indicates all gross clinical disease; R2 indicates inability to completely excise all clinical disease (i.e. gross residual tumor unable to be removed at surgery).

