# **10 STATISTICAL CONSIDERATIONS**

The primary endpoint of pathologic response including pCR is expected to be seen in 30% of patients, hence 6 of the planned 20 patients are expected to have a pathologic response, including pCR.

Pathological response will be determined by assessing the tumor viability at baseline and at surgery. Samples will be scored as a percentage viability (0-100%). A pathologic complete response (pCR) will be defined as no viable residual melanoma cells in the surgical specimen. A major pathologic response will be defined as <50% viable tumor cells. A minor pathologic response will be defined as 50% or greater viable tumor cells, including specimens that have 100% viability at surgery. Pathologic response rate (pRR) will be defined as frequency of either pCR or a major pathologic response. Analysis will also be performed of baseline tumor biopsies and on treatment biopsies if available for comparisons with the surgical resection specimen.

The null hypothesis is that the pathologic response rate for patients receiving the treatment is 5% or less. The alternative hypothesis is that the pathologic response rate is 30%. With 20 evaluable patients there will be 59% power using an exact binomial test at the one-side 0.05 significance level if the true response rate is 20%, and 89% power at one-sided alpha = 0.05 if the true response rate is 30%. Four or more pathologic responses in up to 20 patients will be sufficient to reject the null hypothesis. In additional to the statistical test, a 95% exact binomial confidence interval for the pathologic response rate will be calculated.

Kaplan-Meier methods and associated confidence intervals will be used to analyze RFS and OS. All subjects assessed for relapse will contribute to this analysis.

The statistical analysis of the safety data will be descriptive and tabular in nature.

The statistical analysis of pathologic and correlative exploratory endpoints will be descriptive. No hypothesis tests will be performed for exploratory endpoints.

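### Treated patients who stop early or are not resected leave the primary denominator whatever the reason, and no response rate among all treated patients is planned beside the evaluable-only rate

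*Combined protocol and SAP*

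**What the plan says.** Three sections define who counts for the primary endpoint.

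- Section 4.2 treats as evaluable only patients who get both agents and are resected on the calendar's schedule. It adds: "Patients who discontinue the study before surgery then will be considered non-evaluable and will be replaced per principal investigator discretion".
- Section 6.1.2: "Patients who cannot proceed to surgery will not be evaluable and will be replaced". Here replacement reads as automatic, whereas in 4.2 it is discretionary.
- Section 9.1: "A patient must complete the neoadjuvant phase of the trial and complete surgery to be considered evaluable for pathological response".

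None of them makes an exception by reason. Section 6.5 lists, among the grounds for compulsory withdrawal from study treatment, "Adverse events incurred from intra-tumoral administration of the study agent" (with examples of grade 3 or worse) and death. Section 7.1.2 adds: "If the patient is unable to tolerate the reduced dose the patient will be withdrawn from treatment".

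Section 10 states: "The null hypothesis is that the pathologic response rate for patients receiving the treatment is 5% or less". It then bases power on 20 evaluable patients and plans one exact binomial test and one exact 95% interval. It names no rate among all treated patients, no rule for patients without a surgical specimen, and no sensitivity analysis.

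Section 6.1.2 lets unoperated patients stay on study treatment at the principal investigator's discretion, and note 19 to the study calendar says "Only RECIST will be used as clinical response criteria and used to make treatment decisions". Neither returns such patients to the primary denominator.

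**The concern.** In a single-arm trial the response rate and its interval are the main efficacy result. Patients enter with resectable disease, so losing the chance of surgery through progression, toxicity or death is a failure of the neoadjuvant strategy. Under the plan such a failure cannot lower the reported rate, because the patient is removed and can be replaced.

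The exclusion has two parts. The first is treated patients who never have surgery. The second follows from the requirement in 9.1 to complete the neoadjuvant phase and the requirement in 4.2 to be resected on schedule: a patient who stops early, for instance for HF10 intolerance, and is then resected is also non-evaluable, even though a specimen exists.

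At stake is what the published percentage describes. A reader who takes the wording of the null at face value would apply the rate to patients starting treatment, when it describes those who finished it and were operated on.

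**Working it through.** **Inputs from section 10.** 20 evaluable patients; null 5%; alternative 30%; one-sided 0.05; reject at 4 or more responses; 6 of 20 responses expected at 30%.

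**Not in the documents.** The share of treated patients not resected, d. I assume 5% to 20% and extend to about 30% to find where the test would be affected. Section 5.1.2 requires disease eligible for complete resection, so d may be small.

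**Step 1: the plan's own figures.** With X binomial (20, p):
- P(X≥4) at p = 0.20 is 0.589 (plan: 59%).
- P(X≥4) at p = 0.30 is 0.893 (plan: 89%).
- P(X≥4) at p = 0.05 is 0.0159. P(X≥3) would be 0.0755, so 4 is the right cut-off.

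**Step 2: unresected patients added back as non-responders.** Keep 20 evaluable patients and add m replaced, unresected patients. The rate is x/(20+m), with a Clopper-Pearson interval. The last column is the one-sided exact p-value for 4 responders against 5%.

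| m | Treated | Share unresected | 6 responders (95% CI) | 4 responders (95% CI) | p for 4 |
|---|---|---|---|---|---|
| 0 | 20 | 0% | 30.0% (11.9-54.3) | 20.0% (5.7-43.7) | 0.0159 |
| 1 | 21 | 4.8% | 28.6% (11.3-52.2) | 19.0% (5.4-41.9) | 0.0189 |
| 2 | 22 | 9.1% | 27.3% (10.7-50.2) | 18.2% (5.2-40.3) | 0.0222 |
| 5 | 25 | 20.0% | 24.0% (9.4-45.1) | 16.0% (4.5-36.1) | 0.0341 |
| 8 | 28 | 28.6% | 21.4% (8.3-41.0) | 14.3% (4.0-32.7) | 0.0491 |

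With 29 treated the p-value for 4 responders is 0.0548. At the smallest positive result, the two-sided 95% interval excludes 5% for 4/20 but not for 4/25, although the one-sided test at 0.05 still rejects. These intervals and p-values take the number treated as fixed. That is an approximation when patients are added until 20 are evaluable.

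**Step 3: the same in expectation.** If only unresected patients are excluded and they count as non-responders, the evaluable-only rate is p/(1-d). An all-treated 30% then reads as 0.30/0.95 = 31.6%, 0.30/0.90 = 33.3% or 0.30/0.80 = 37.5% at d = 5%, 10% or 20%.

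**Step 4: the decision rule.** If the all-treated rate is 5%, the false-positive probability of the planned rule is P(X≥4) at p = 0.05/(1-d). It is 0.0189, 0.0226 and 0.0330 at d = 5%, 10% and 20%, and reaches 0.05 only at d of about 30%.

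**Step 5: patients resected after stopping early.** Their pathology can be observed, and some may be responders, so p/(1-d) does not cover them. In general the all-treated rate is (6+r)/(20+m), where m is everyone excluded and r the responders among them. It falls below 30% only when r/m is below 30%. With m = 5, for example, r = 0 gives 6/25 = 24%, r = 1 gives 7/25 = 28%, and r = 2 gives 8/25 = 32%.

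**The case against.** The evaluability rule is an openly stated design choice, repeated in three sections and carried into the sample size. The endpoint needs a surgical specimen, so an unresected patient has no observed value. Counting that patient as a non-responder is a convention, and a harsh one for someone who declines surgery for unrelated reasons. Read in context, the 5% and 30% most naturally refer to evaluable patients, because the power statement for 20 evaluable patients follows directly. At 5% to 10% unresected, the shift is small against an interval about 42 percentage points wide. Failures are also not invisible: pre-surgical RECIST response, adverse events and overall survival are not expressly limited to resected patients.

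Most of this stands. It is why the evaluable-only rate should remain primary and the all-treated rate be supportive. It does not remove the gap. None of those other endpoints gives a pathologic response rate among treated patients, and recurrence-free survival (9.3) starts at complete resection, so it omits unresected patients as well. A reader could rebuild the all-treated rate only if the number treated and the reasons for non-evaluability were reported, and section 10 commits to neither.

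A reader might infer more than the documents support:

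- **That the test is invalid.** Steps 2 and 4 show otherwise. The exact type I error of 0.016 leaves enough slack for up to 8 replaced patients.
- **That the evaluability text names progression, toxicity or death.** It does not. They are covered because the wording is unqualified, and 6.5 and 7.1.2 require withdrawal from treatment without barring surgery.
- **That everyone operated on is counted.** Sections 4.2 and 9.1 say otherwise for early stoppers. Section 9.8 states that "R2 indicates inability to completely excise all clinical disease" but is silent on evaluability, so the place of R2 patients in the denominator is an inference.
- **That treatment failures must not be replaced.** That would change the primary population and cost power. If 30% is the rate among resected patients, P(X≥4) with 20 treated falls from 89% to 83% at d = 10% (p = 0.27) and 74% at d = 20% (p = 0.24).

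**Conclusion.** The concern holds as a gap in estimation and reporting. The plan yields one rate and one interval, in a set from which treatment failures can drop out for any reason, while its null is worded for treated patients. Under the convention that unresected means non-responder, and with an assumed 5% to 20% unresected, an observed 30% overstates the all-treated rate by about 1 to 6 percentage points. The true share is unknown, and with few unresected patients the effect is minor. Patients resected after stopping early could move the all-treated rate either way. The decision rule of 4 or more in 20 can stand. The change is worth making because it costs almost nothing and tells the reader what the headline rate describes.

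**What to change.** Add to section 10, in substance:

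> As a supportive analysis, the pathologic response rate will also be reported with its exact 95% confidence interval among all patients who received any nivolumab or HF10. Observed pathology will be used for every resected patient, including those who stopped neoadjuvant treatment early; unresected patients will be counted as non-responders, a conservative convention. The number of non-evaluable patients will be given by reason: progression, toxicity, death, refusal, other.

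Leave the evaluable-only test, its cut-off and the replacement rule unchanged.

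The cost is a short addition to section 10, a recorded reason for each non-evaluable patient, and the same viability reading for specimens from patients who stopped early. No extra patients are needed and power is unaffected. The downside is that a slightly lower rate will probably appear beside the primary one.
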